9.4.3 ANALYSIS OF THE SECONDARY ENDPOINT(S)

Aim 1 will also test the secondary null hypotheses that there is no difference in the least-squares mean estimate of the change in Wolf-Motor Functional Test (WMFT) time score and Stroke Impact Scale (SIS, version 3) hand subscale at day 15. The procedure described above will be repeated for each of the secondary endpoints with the type-I error rate adjusted using a Bonferroni type gate-keeping procedure to sequentially test the hierarchical null hypotheses^{120, 121}. That is, if the primary null hypothesis (i.e., no difference in the change in FM-UE Scale between the three groups) is rejected, the secondary null hypothesis of no difference with respect to WMFT time score will be assessed; if that null hypothesis is also rejected, then the null hypothesis of no difference in the SIS hand subscale will be tested.

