of FM-UE scale⁹¹ from patients included in the EXCITE trial was 42.5 (SD 11.7) for the CIMT group and 41.1 (SD 12.9) for the usual care group. Thus, even a patient with an FM-UE score of around 30 was eligible for the EXCITE trial¹⁹. Furthermore, we are planning to include patients that correspond to both the higher and lower functioning groups in the EXCITE trial to have as many eligible subjects as possible. However, the baseline disability will be adjusted for in both the randomization and analysis to ensure that the treatment groups are balanced. The lower-functioning subjects in the EXCITE trial had at least 10° of active wrist extension, at least 10° of thumb abduction/extension, and at least 10° of extension in at least 2 additional digits. Higher-functioning subjects demonstrated at least 20° of wrist extension and at least 10° of active extension of each metacarpophalangeal and interphalangeal joint of all digits¹⁹. The assembled TRANSPORT2 team include several key personnel from the EXCITE and VECTOR trial to ensure that mCIMT, the peripheral rehabilitation therapy in our TRANSPORT2 trial, is done with the highest level of consistency across sites. Using a standardized intervention and providing experienced trainers and oversight for other sites, will minimize the variance that a peripheral rehabilitation therapy could introduce, and it will increase the odds to detect efficacy from tDCS.

A.5. Timing of the proposed intervention

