8 STUDY ASSESSMENTS AND PROCEDURES

8.1 EFFICACY ASSESSMENTS

Primary Objectives (Efficacy Outcomes): To determine whether there is an overall intervention effect among 3 dosing groups (sham+mCIMT, 2 mA+mCIMT, and 4 mA+mCIMT) at day 15 after initiation of the intervention in the Fugl-Meyer Upper-Extremity (FM-UE) scale¹⁰⁶, a measure of motor impairment. FM-UE scale consists of a 33-item assessment which provides a global assessment of UE motor impairment. A rater observes 30 voluntary UE motions and 14 voluntary LE motions, 6 tendon tap responses, and provides an ordinal rating (2=near normal ability/response, 1=partial ability, 0=unable to perform/no response). FM-UE scale is a proven scale with excellent intra-rater reliability (0.99), inter-rater reliability (0.99), test-retest reliability (0.94 –0.99), and internal consistency (0.97).¹⁰⁷⁻¹⁰⁹

Secondary efficacy outcome measures include the Wolf-Motor-Function-Test (WMFT)¹¹⁰⁻¹¹², a measure of functional motor activity, and the Stroke-Impact-Scale (SIS)¹¹³, a measure of the quality of life at day 15 after initiation of the intervention. These efficacy outcomes will be collected at the baseline, day 15, day 45 and day 105. WMFT quantifies upper extremity (UE) motor ability through timed and functional tasks. It is a 17-item assessment providing a measure of UE functional ability. In this test, participants are timed as they complete 17 tasks that involve movements and interactions with objects (e.g., placing hand on table, picking up a soda can). These activities begin with those involving only shoulder movements and progress to those requiring distal control of fine motor movements. In addition, subject's movement will be assessed for meeting “**Essential Elements**” (specific elements) that must be accomplished in order for the task to be deemed complete” vs. “**Desired Elements**” which are other qualitative elements that should be included in the task but are not necessary for completion” (please refer to details in the Outcome Assessments MOP, located in the WebDCU Toolbox).¹¹⁵

SIS is a stroke-specific, self-report, health status measure assessing multidimensional stroke outcomes.^{113, 114} The current 3.0 version includes 59 items and assesses 8 domains: strength (4

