9 STATISTICAL CONSIDERATIONS

9.1 STATISTICAL HYPOTHESES

- Primary Efficacy Endpoint(s):

The primary null hypothesis is that there is no difference in the least-squares mean estimate of the change in FM-UE scale on Day 15 after the initiation of the 14 day intervention among the three dose groups.

$$H_0: \hat{Y}_{sham,15d} = \hat{Y}_{2mA,15d} = \hat{Y}_{4mA,15d}$$

H_A : The means are not all equal

- Secondary Efficacy Endpoint(s):

The secondary null hypothesis is that there is no difference in the least-squares mean estimate of the change in Wolf-Motor Functional Test (WMFT) time score and Stroke Impact Scale (version 3.0, SIS) hand subscale.

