In addition, with a sample size of 31 subjects per group, a two-sided type I error rate of 10%, and standard deviation of 7, if the true pattern of mean changes is 4.5, 9.0, and 9.0 for the sham, 2 mA, and 4 mA groups respectively, we would have 83% power to reject the null hypothesis. A 10% type I error rate was selected in consideration of the track record for safety in the intervention, the relative cost of committing a type I and type II error with respect to trial duration, subject utilization, and the remaining need for a subsequently planned Phase III trial should the current trial demonstrate promising results. Based on a conservative estimate from the EXCITE and VECTOR trial^{14, 19}, 8% of subjects are expected to complete less than 10 full sessions of tDCS + mCIMT in the specified 14 day time-window. Thus, the sample size is inflated for the cross-over in treatment effect using an inflation factor of $1/(1-0.08)^2$.¹¹⁷ In addition, up to 15% of subjects may be lost to follow-up prior to collection of the primary outcomes at the 3-month follow-up visit.

Therefore, an inflation of 115% is used to account for the missing samples in the ITT primary analysis. As a result, the final estimated sample size is 43 per group (or 129 subjects in total). Finally, considering the longitudinal nature of the design and adjustment for key covariates, the power will be maintained when using an auto-regressive (1) correlation structure regardless of the degree of correlation between FM-UE scale measured on proximal visits or the strength of the covariates as predictors. We elected not to further reduce the sample size both because a robust estimate of these quantities is not currently available, and to retain sufficient power to evaluate secondary hypotheses.

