9.4 STATISTICAL ANALYSES

Details of the statistical analyses are provided in the Statistical Analysis Plan.

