9.4.2 ANALYSIS OF THE PRIMARY EFFICACY ENDPOINT(S)

The change in FM-UE Scale in each treatment arm will be modeled using generalized linear mixed effects repeated measures model, where the dependent variable is the change from baseline in

FM-UE to post-intervention visit; the model is adjusted for intervention arm, baseline FM-UE, time from stroke, visit and site; and the primary outcome is the fitted estimate at day 15. Model assumptions, including normality, will be assessed and appropriate transformations will be used in keeping with best practices and conventional approaches in the literature. If the primary null hypothesis is rejected, all pairwise secondary hypotheses will be tested using a Dunnett type multiple comparisons correction^{118, 119}.

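### Section 9.4.3 does not say whether the WMFT and SIS models adjust for the endpoint's own baseline; read literally they adjust only for baseline FM-UE and lose some precision

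*Combined protocol and SAP*

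**What the plan says.** Section 9.4.2 describes a repeated-measures mixed model "where the dependent variable is the change from baseline in" FM-UE, and lists its terms: "the model is adjusted for intervention arm, baseline FM-UE, time from stroke, visit and site". FM-UE is the only baseline score in that list.

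Section 9.4.3 gives the secondary endpoints no covariate list of their own: "The procedure described above will be repeated for each of the secondary endpoints". It then sets the testing order. WMFT time is tested if the FM-UE null is rejected, and SIS hand is tested if the WMFT null is also rejected. Section 9.1 defines both secondary endpoints as changes: "The secondary null hypothesis is that there is no difference in the least-squares mean estimate of the change in Wolf-Motor Functional Test (WMFT) time score", with the SIS hand subscale named alongside.

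The baseline values exist. Section 8.1 says of the efficacy outcomes: "These efficacy outcomes will be collected at the baseline, day 15, day 45 and day 105". The schedule in 1.3 places WMFT and SIS at Baseline 2.

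Two other statements bear on the point. Section 2.2 says that "the baseline disability will be adjusted for in both the randomization and analysis", and 6.3 lists the balancing covariates as site, time from stroke and baseline FM-UE. Section 9.4 says: "Details of the statistical analyses are provided in the Statistical Analysis Plan".

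**The concern.** Baseline FM-UE does two jobs in the primary model. It is the endpoint's own baseline, and it is a covariate used in the allocation algorithm. For WMFT and SIS these jobs fall to different variables, and 9.4.3 does not say which is meant. Three models fit the text: baseline FM-UE only, own baseline in place of FM-UE, or both. They give different standard errors and can give different p-values for endpoints tested in a fixed order.

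The literal reading is the least efficient. A change score that is not conditioned on its own baseline keeps regression to the mean in the residual. Baseline WMFT and SIS are not balanced by the randomization, except so far as they track FM-UE.

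Precision on these endpoints matters to the plan. Section 9.2 declines to reduce the sample size partly to keep power for secondary hypotheses. Section 2.2 (A8) allows that an outcome other than FM-UE may become primary in phase III. WMFT also decides whether SIS is tested at all.

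**Working it through.** **The plan's own figures.** Section 9.2 states 83% power "with a sample size of 31 subjects per group, a two-sided type I error rate of 10%, and standard deviation of 7", for mean changes of 4.5, 9.0 and 9.0.
- Grand mean 7.5; squared deviations 9 + 2.25 + 2.25 = 13.5.
- Noncentrality 31 × 13.5 / 49 = 8.54, giving F-test power of 82.8%, which agrees with the plan.
- Sample size: 31 / 0.92² = 36.6; × 1.15 = 42.1; rounded up to 43 per arm, 129 in total. This also agrees.

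These figures concern FM-UE only. The documents state no SD or power for WMFT or SIS, so no published figure changes.

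**Cost of the literal reading.** Let r be the correlation of the endpoint's baseline with its day-15 value, and q its correlation with baseline FM-UE. The sign of q does not matter, because it enters squared. Assume equal SDs at both times, scaled to 1, and that FM-UE is related to the day-15 score only through the endpoint's own baseline.

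- Variance of change: 2 − 2r.
- Covariance of change with baseline FM-UE: qr − q = −q(1 − r).
- Residual variance, FM-UE only: 2(1 − r) − q²(1 − r)² = (1 − r)[2 − q²(1 − r)].
- Residual variance, own baseline plus FM-UE: 1 − r² = (1 − r)(1 + r).
- Variance ratio, with own baseline over without: (1 + r) / [2 − q²(1 − r)].
- Relative standard error without own baseline: 1 / √ratio.

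| r | q | Variance ratio | Standard error without own baseline |
|---|---|---|---|
| 0.5 | 0.4 | 1.5 / 1.92 = 0.78 | +13% |
| 0.5 | 0.8 | 1.5 / 1.68 = 0.89 | +6% |
| 0.7 | 0.4 | 1.7 / 1.952 = 0.87 | +7% |
| 0.7 | 0.8 | 1.7 / 1.808 = 0.94 | +3% |
| 0.9 | 0.4 | 1.9 / 1.984 = 0.96 | +2% |
| 0.9 | 0.8 | 1.9 / 1.936 = 0.98 | +1% |

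**In terms of power.** Take, hypothetically, a secondary test with the plan's 83% power when own baseline is included. Without it, power is about 74% at q = 0.5, r = 0.5; 78% at q = 0.5, r = 0.7; and 82% at q = 0.8, r = 0.9.

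**What the documents cannot supply.** Neither r nor q appears. The one WMFT correlation given (−0.62, section 2.2, A8) is between the changes in FM-UE and WMFT, so it is neither of these. The calculation uses a single post-baseline visit and ignores information from days 45 and 105.

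**Cost of the replacement reading.** Under the assumption above, FM-UE adds nothing once own baseline is in the model, so this calculation puts no price on dropping it. The reason to keep it is the design: 6.3 uses it in allocation, and 2.2 commits to adjusting for baseline disability in the analysis.

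**The case against.** The strongest reply is that 9.4.2 is a template. It cannot be repeated word for word, because its dependent variable is change in FM-UE. An analyst who puts WMFT in the outcome would naturally put WMFT in the baseline term too, and the omission disappears. The detail may also sit in the SAP to which 9.4 defers. Both points stand. A reader might infer that the secondary endpoints are definitely analysed without their own baselines, and the documents do not support that. They leave the matter open. But the substitution reading does not close the question either, since it silently drops a balancing covariate.

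Three further inferences should be resisted.

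- *That the contrast is biased by baseline imbalance.* Randomization keeps it unbiased on average, and chance imbalance is already part of the standard error. The SD of the chance baseline difference between two arms of 43 is √(2/43) = 0.216 baseline SD. At r = 0.7 a wholly unadjusted change score carries 30% of it, or 0.065 SD. That is not the model here: with FM-UE included, multiplying by √(1 − q²) for q = 0.4 to 0.8 leaves about 0.06 to 0.04 SD.
- *That lost precision closes the gate to SIS.* A larger standard error lowers the chance that WMFT passes; it does not prevent it.
- *That the loss is demonstrated.* It rests on assumed correlations. The 13% figure needs r = 0.5 over about two weeks together with q = 0.4, and at r = 0.9 the loss is only 1% to 2%.

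**Conclusion.** The point holds as a gap in specification with a modest, conditional cost. Section 9.4.3 does not determine the baseline covariates for two hierarchically tested endpoints, and its literal reading is the less efficient one. Under that reading the standard error of the day-15 contrast is about 1% to 13% larger, given r of 0.5 to 0.9, q of 0.4 to 0.8, equal variances and a single follow-up visit. Under the replacement reading a randomization covariate is lost from the model. The primary analysis, the 83% power and the 129 subjects are unaffected. If the SAP already names the own baselines alongside FM-UE, all that remains is to align 9.4.3 with it.

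**What to change.** Add to 9.4.3, and align the SAP before unblinding so that covariates are not chosen after results are seen: *The model for each secondary endpoint includes that endpoint's own baseline value as a covariate, in addition to baseline FM-UE, time from stroke, visit and site.* The intervention-arm term stays as in 9.4.2.

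This improves the model whichever reading was intended. Under the literal reading it adds a baseline that is already collected; under the replacement reading it keeps the balancing covariate. The cost is one degree of freedom per model, with no new data and no change in sample size.

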9.4.4 SAFETY ANALYSES

Safety: Analysis Method

IMSM and Data and Safety Monitoring Board (DSMB) will receive periodic safety reports of all reportable adverse events including serious adverse events (SAEs) if there are any. All clinical safety endpoints and SAEs will be summarized by AE code (as provided on the AE CRF) regarding the frequency of the event, the number of subjects having the event, severity, and relatedness to the study treatment. Clinically important adverse events include:

- Severe headache
- Second-degree skin burn
- Clinical seizure
- Neurological deterioration (\geq 4-point increase in NIHSS)

The proportion of subjects experiencing each of these events will be provided in the closed report by intervention arm with two-sided 95% CIs and unadjusted relative risks. Based on the Phase I dose-escalation study, no subjects experienced any of the clinically important adverse events. Fisher's exact tests will be used to assess intervention group differences in the rates of clinically important adverse events.

Tolerability: Analysis Method

Tolerability will primarily be measured through the use of the Visual-Analog scale (VAS), a 10-point scale ranging from 0 (No Discomfort) to 10 (Extreme Discomfort). For the primary analysis, any subject who requests to be withdrawn from the study due to procedure related issues will be imputed as a 10 on the Visual-Analog Scale. Differences in tolerability will be assessed using a Kruskal-Wallis test at a 10% type-I error rate.

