1 PROTOCOL SUMMARY

1.1 SYNOPSIS

Title: TRANScranial direct current stimulation for PPost-stroke motor Recovery- a phase II sTudy (TRANSPORT2)

Study Description: TRANSPORT2 is a phase II multi-center transcranial direct current stimulation (tDCS) dosing selection study based on the preliminary efficacy, safety, tolerability and feasibility.

Objectives: **Primary Objective:** To determine whether there is an overall treatment effect among 3 dosing groups (sham+mCIMT, 2 mA+mCIMT, and 4 mA+mCIMT) on day 15 (\pm 2 days) after the start of the intervention in the Fugl-Meyer Upper-Extremity (FM-UE) scale, a measure of motor impairment. Additional outcome measures include the Wolf-Motor-Function-Test (WMFT), a measure of functional motor activity, and the Stroke-Impact-Scale (SIS), a measure of quality of life. Sustained benefit will be assessed at day 45 (\pm 5 days) and day 105 (\pm 10 days).

Secondary Objectives: To confirm that the proposed intervention is safe (no significant differences in rate of adverse events), tolerable (no significant differences in discomfort as measured by Visual-Analog-Scale), and feasible to administer in a multi-site trial (>80% of subjects complete the treatment protocol and no unexplained/unresolved variability by site).

Exploratory Objectives: To examine whether wCST-LL (structural assessment of integrity of descending motor tract) or MEPs (functional assessment of integrity of descending motor tract) or combination of both are correlated with changes in FM-UE scale, and evaluate the utility of these measures as biomarkers for patient selection criteria in the future confirmatory Phase III study. We also

aim to examine whether structural and functional changes within descending motor tracts correlate with changes in motor impairment and functional motor activity.

Endpoints:

Primary Endpoint: Fugl-Meyer Upper-Extremity (FM-UE) scale a measure of motor impairment;

Secondary Endpoints: Wolf Motor Function Test (WMFT) time score, a measure of functional motor activity; Stroke-Impact-Scale hand subscale as an assessment of patient-centered quality of life.

Study Population:

Subject who is 18-80 years of age of any gender or ethnicity, who had first-ever unihemispheric ischemic stroke in past 30-180 days resulting in unilateral limb weakness with FM-UE ≤ 54 (out of 66) that is stable across two baseline visits at the time of randomization and an mRS ≤ 2 pre-stroke. We are planning to enroll 129 subjects across three arms.

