While underdosing is possible, lack of published data at higher currents and theoretical concerns of safety has led researchers to avoid higher tDCS current than 2 mA in stroke patients. A meta-analysis indeed showed a dose-response relationship with motor improvement and current up to 2 mA³⁹. **The Phase I current escalation study of tDCS (PI [name], NINDS P20 GM109040) found that doses up to 4 mA are safe and tolerable to ischemic stroke patients (manuscript is highlighted in the Brain Stimulation Journal cover page and accompanied by an editorial)**^{85, 86}. There were no second-degree skin burns, clinical seizures, or DWI abnormalities. Furthermore, no subjects discontinued from the trial. Thus, while this phase I study suggests that doses up to 4 mA are safe and tolerable, it is not clear whether a dose-response relationship in treatment effect would extend beyond 2 mA. It is a logical next step to test a dose effect in a phase II multicenter study while we continue to collect data on safety and tolerability.

A.4. The choice of a peripheral rehabilitation therapy

Several studies have shown that the combined effects of tDCS or other non-invasive brain stimulation technique and a peripheral rehabilitation therapy typically elicit behavioral changes and subsequent improvement of motor functions greater than when either intervention is done by itself^{35-37, 42, 87}. If the variance and effect (or the duration and intensity) from peripheral rehabilitation therapy is not well controlled and balanced across the groups, the real effect from tDCS is likely contaminated and attenuated. For example, various peripheral rehabilitation therapies have been tested in combination with tDCS such as customary occupational/physical therapy^{36, 88}, robot-assisted therapy⁸⁹ and virtual reality therapy³⁸. Although we do know from experimental studies that combining peripheral stimulation with central stimulation will increase synaptic plasticity, it is harder to determine whether tDCS in combination with untested peripheral rehabilitation is efficacious as the efficacy of these peripheral rehabilitation therapies by themselves have not been proven²¹.

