2.3 RISK/BENEFIT ASSESSMENT

2.3.1 KNOWN POTENTIAL RISKS

- **General Risk Loss of Confidentiality:** It is expected that this risk will be low because of numerous safeguards that will be in place, including standard data management procedures at the NDMC.
- **tDCS:** Extensive animal and human evidence and theoretical knowledge indicate that tDCS protocols up to 2 mA are safe and tolerable⁷⁵⁻⁷⁷. Recently, a Phase I study evaluated the safety and tolerability of tDCS doses up to 4mA in patients with ischemic strokes; the study used a 3+3 study design and escalate dose to 4mA without meeting pre-specified safety rules. Overall, tDCS incurs no significant risk to human subjects per FDA determination. Commonly reported side effects in the literature are as follows: skin redness under the electrode, skin irritation with itching, tingling, burning sensation, and transient headache (which is mostly due to the tight elastic headband that holds the electrode in place). Any skin injury is a very rare side effect (1 out of 1000). Theoretical risks at high dose (e.g., 4mA) might involve second degree skin burns and clinical seizures, but these risks were not observed in the phase 1 safety study. Subjects will be carefully monitored for any potential safety or tolerability issues during each interventional session.

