4 STUDY DESIGN

4.1 OVERALL DESIGN

The **TRANSPORT2 (TRANScranial direct current stimulation current for Post-stroke mOtOr Recovery – a phase II sTudy)** trial will test an **overall hypothesis** that a combination of bihemispheric tDCS stimulation at 2 mA or 4 mA, along with mCIMT, will lead to a greater sustained motor improvement on day 15 (± 2 days) after the start of the intervention as compared to sham stimulation. Sustained benefits will be assessed at day 45 (± 5 days) and day 105 (± 10 days) after the start of the intervention. This multicenter, phase II, sham-controlled 3-arm study will randomize 129 subjects in a 1:1:1 allocation ratio per arm (sham, 2 mA, or 4 mA tDCS), and treat subjects with the assigned dose of tDCS for 30 minutes (± 6) and mCIMT for 120 minutes (± 24) of active time, for 10 sessions over a 14 day period. However, the total time of mCIMT will be less than 150 minutes.

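### In 9.4.4 the only between-arm effect estimate for the clinically important adverse events is a relative risk, which often cannot be computed against sham with 43 subjects per arm

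*Combined protocol and SAP*

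**What the plan says.** Section 9.4.4 lists four clinically important adverse events: severe headache, second-degree skin burn, clinical seizure, and a rise of at least 4 points on the NIHSS. It specifies three summaries for them:

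- the proportion of subjects affected in each arm, with a confidence interval;
- relative risks: the proportions "will be provided in the closed report by intervention arm with two-sided 95% CIs and unadjusted relative risks";
- a test: Fisher's "exact tests will be used to assess intervention group differences in the rates of clinically important adverse events".

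Between the second and third items it reports: "Based on the Phase I dose-escalation study, no subjects experienced any of the clinically important adverse events". Section 2.2 (A.3) says much the same of Phase I: "There were no second-degree skin burns, clinical seizures, or DWI abnormalities". Section 2.3.1 puts the frequency of any skin injury with tDCS at 1 in 1000.

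Section 9.4.4 names no reference arm for the relative risk, no rule for an arm without events, no risk difference and no significance level for Fisher's test. Section 4.1 says the trial "will randomize 129 subjects in a 1:1:1 allocation ratio per arm", and section 9.2 gives 43 per group. Section 9.4 defers analysis detail to a Statistical Analysis Plan, whose separate text was not in the material available for this review.

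**The concern.** A relative risk needs at least one event in the reference arm. Sham is the natural reference, although the plan does not say so. If sham has no events, the relative risk is infinite when the active arm has some and 0/0 when it has none. The usual interval on the log scale does not exist in either case. The 4 mA versus 2 mA ratio fails in the same way if the 2 mA arm has no events.

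This is a dose-selection study that takes the current up to 4 mA, and the synopsis defines safety as the absence of significant differences in adverse event rates. With few events and 43 per arm, a non-significant test is weak evidence of safety. What helps the DSMB, and whoever plans Phase III, is an interval showing how much excess risk at 2 mA or 4 mA the data still allow. As written, the only planned estimate that could carry such an interval is the one most likely to be missing.

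**Working it through.** **Inputs**
- 43 subjects per arm (9.2; 129 in total at 1:1:1 in 4.1).
- Rate of any skin injury: 0.001 (2.3.1). This is not arm-specific and bears on only one of the four events.
- Other true rates of 0.5%, 1% and 2% are assumptions. The protocol gives no sham rate for severe headache, seizure or NIHSS worsening.

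**1. The plan's sample size.** One-way ANOVA, 31 per group, means 4.5, 9.0 and 9.0, SD 7, two-sided alpha 0.10. The noncentrality is 31 × (9 + 2.25 + 2.25)/49 = 8.54, which gives 82.8% power (stated: 83%). Inflation: 31/(0.92)² = 36.63; × 1.15 = 42.1, rounded up to 43 (stated: 43). This confirms the number per arm and nothing more.

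**2. Chance of no sham events.** P(0 of 43) = (1 − p)^43:
- p = 0.1% (documents): 95.8%
- p = 0.5% (assumed): 80.6%
- p = 1% (assumed): 64.9%
- p = 2% (assumed): 41.9%

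Closed reports are semiannual (8.2.4), so early ones will hold fewer subjects. With, say, 21 per arm, about half of full enrolment, the figures at 1% and 2% are 0.99^21 = 81% and 0.98^21 = 65%.

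**3. Relative risk with a 0.5 correction, for 3/43 against 0/43.** RR = (3.5/44)/(0.5/44) = 7.0. SE of log RR = √(1/3.5 − 1/44 + 1/0.5 − 1/44) = 1.497. The 95% CI is 7.0 × exp(±1.96 × 1.497) = 0.37 to 132.

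**4. Risk difference (Newcombe), same data.** The Wilson limits are 2.4% to 18.6% for 3/43, and 0 to 3.84/(43 + 3.84) = 8.2% for 0/43. The difference is 7.0 points.
- Lower limit: 7.0 − √((7.0 − 2.4)² + 8.2²) = −2.4
- Upper limit: 7.0 + (18.6 − 7.0) = 18.6

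**5. Other counts, sham 0/43**

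| Active arm | Relative risk | RR with +0.5 (95% CI) | Risk difference in points (Newcombe 95% CI) | Two-arm Fisher p |
|---|---|---|---|---|
| 0/43 | 0/0 | 1.0 (0.02 to 49) | 0.0 (−8.2 to 8.2) | 1.00 |
| 1/43 | infinite | 3.0 (0.13 to 72) | 2.3 (−6.1 to 12.1) | 1.00 |
| 3/43 | infinite | 7.0 (0.37 to 132) | 7.0 (−2.4 to 18.6) | 0.24 |
| 5/43 | infinite | 11.0 (0.63 to 193) | 11.6 (1.1 to 24.5) | 0.055 |

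The corrected relative risk is finite but says almost nothing. The risk difference is defined in every row.

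**The case against.** The strongest reply is that the relative risk is only one of several planned summaries and the rest work with no sham events. Each arm's proportion comes with its own interval (0/43: exact 95% CI 0 to 8.2%). Fisher's exact test across the three arms gives p = 0.11 for counts of 0, 0 and 3, and p = 0.034 for 0, 0 and 4. The DSMB would see directly that events fell only in an active arm, and it may unblind itself (8.2.4). The point estimate of a risk difference is a subtraction of proportions already shown. All of this stands. A reader might infer from the relative-risk wording that the DSMB would have no usable comparison between arms; the documents do not support that. The real gain is an interval for the difference, which neither the per-arm intervals nor a p-value supplies.

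A reader might also infer that the protocol expects no sham events. It reports a Phase I result and predicts no count for this trial. Severe headache or neurological worsening could occur in any arm, and at an assumed 2% rate no sham events is less likely than not (42%).

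A third tempting step is to call Fisher's test wrong for ignoring the order of the currents and to ask for a trend test. By exact enumeration at 43 per arm and two-sided 5%, for assumed rates in sham, 2 mA and 4 mA:
- 0/2/8%: trend 41%, Fisher 31%
- 0/0/8%: 45% for both
- 0/8/8%: trend 22%, Fisher 30%

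The advantage depends on the shape assumed. A second p-value would also invite a choice between tests against the synopsis criterion of no significant differences. Fisher's test is a legitimate choice.

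**Conclusion.** The point holds, at minor severity. Section 9.4.4 names one between-arm effect estimate, and for an event with a true sham rate of 1% or less that estimate has a 65% or higher chance of being infinite or undefined at full enrolment. A risk difference with an interval is defined in all these cases.

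This rests on four things: sham as the reference arm, which is the natural reading but unstated; 43 subjects per arm; event rates that are assumed except for the 1-in-1000 figure; and the absence of a zero-event rule or risk difference in the separate SAP, which could not be checked. It does not show that the planned safety comparison is invalid or that a dose-related harm would go unseen.

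**What to change.** First check whether the separate SAP already gives risk differences or a rule for arms without events. If it does not, amend 9.4.4 as follows:

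- Make the risk difference the between-arm measure in the closed report and the final analysis: 2 mA minus sham, 4 mA minus sham, and 4 mA minus 2 mA. Give each a 95% CI by one named method, Newcombe or Miettinen-Nurminen.
- Show a relative risk only when both arms compared have at least one event, and state the reference arm.
- Keep the per-arm proportions with their intervals and Fisher's exact test. No trend test is needed.

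Two practical notes. Section 8.2.4 has the closed report partially blinded, so the three differences can be labelled with the same arm codes as the proportions. The text should also say that the intervals are descriptive, because they can disagree with Fisher's test: at 5/43 against 0/43 the Newcombe interval excludes zero (1.1 to 24.5) while the two-arm p is 0.055.

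The cost is some wording and a few lines of code. The intervals will be wide: even with no events in either arm, the difference runs from −8.2 to +8.2 points. Sample size and conduct do not change.
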